**Secondary Outcome (Patient Engagement):** We will measure patient engagement in treatment at assessment 1 as well as at assessments 2, 3 and 4. Patient engagement is a complex phenomenon to measure. The term 'patient engagement' encompasses various aspects of care related to a patient's motivation and intent to be an active participant in addressing their healthcare needs. To date, there is no agreed-upon measure in the literature that incorporates all aspects of the experience of 'patient engagement'. In the field of mental health, there is some notion that 'patient engagement' should mean that a patient experiences collaborative care, feels supported during their treatment, and adopts 'good practices' or behaviors that support their overall well-being. Therefore, only assessing whether a patient attended a mental health appointment may not adequately reflect treatment engagement. There is also evidence that symptom severity can preclude patients from engaging in care. Pfeiffer *et al.* found that, despite improvements in timely outpatient follow-up after VA psychiatric hospitalization, there were no significant changes in readmission or antidepressant treatment. In fact, Bernet *et al.* found that appointment intensity was higher in Veterans who reattempted suicide after discharge versus those who did not reattempt. Furthermore, in reviewing our data thus far from our trial on Ground East, we have identified that our current measures of engagement may not be adequately covering a key component of patient engagement as it relates to suicide including self-efficacy around managing suicide risk. This is a key concept that is part of the VA BIC intervention. Thus, we conceptualize that engagement includes patient activation, continuity of care, and self-efficacy.

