- Patient activation: Patient activation is defined as "an individual's knowledge, skill and confidence for managing their health and health care." Individuals who demonstrate higher degrees of patient activation have been found to be more likely to engage in health-promoting behaviors and to experience better outcomes. Because our trial focuses specifically on activation and related self-efficacy in avoiding suicidal behavior after discharge, we will administer the validated Suicide-Related Coping Scale (SRCS). This scale includes 17 questions related to a patient's perception of their ability to cope with suicidal thoughts. Each item is assessed using a 5-point Likert scale and the measure has been developed based on two studies of suicide prevention strategies conducted within Veteran populations. The scale includes two subscales including an External Coping subscale and an Internal Coping Subscale. Both subscales have shown good acceptable internal consistency. The two factors are also sensitive to change over time. Higher scores on the scale suggest better coping.
- Continuity of care: There is some evidence that improved continuity of care may lead to better mental health outcomes. However, a single, valid, standardized measure of continuity of care for mental health has not been described in the literature. Work by Greenberg *et al.* in Veterans who were discharged from a VA inpatient mental health unit provides sufficient evidence that three aspects of continuity of care after psychiatric hospitalization (regularity of care, continuity of treatment across organizational boundaries, and intensity of treatment) are associated with improvements in overall mental health. We will use the three measures of continuity of care as validated by Greenberg *et al.* This includes:
  - a) Continuity of care: Measure of whether a patient discharged from the inpatient MH unit received any MH outpatient treatment in the first month and between 1 – 3 m after discharge.
  - b) Regularity of care: The number of months in the 3 m after the baseline assessment in which the patient attended at least 1 MH visit (Range 0 – 3 m), and
  - c) Intensity of care: Measure of the total number of MH visits between initial entry into the

study and the last study assessment.

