In addition, we will also evaluate evidence of disruptions of care including no-show and cancelled appointments. We will abstract these measures from the electronic medical record. Since it is possible that some patients may receive portions of their care outside of the VA system, we will also ask patients to self-report on non-VA care.

- **Hopelessness**: To gather clinical evidence of treatment engagement, we will assess hopelessness at baseline and at follow-up assessments using the Beck Hopelessness Scale (BHS). The BHS is a 20-item self-report scale that assesses hopelessness over the past seven days. Patients comment on feelings about the future, loss of motivation, and future expectations. Total scores range from 0 to 20, with higher scores suggesting more hopelessness. Higher scores on the BHS are associated with increased suicide risk. The BHS has good reliability and validity and is sensitive to change. The psychometrics of the BHS in the Veteran population have not been studied, but the BHS has been used in other studies of the Veteran population.

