We will calculate 95% CI and *P*-values and will define a *P*-value of < 0.05 to be statistically significant. We will use the maximum likelihood ratio to account for any missing data.

**Specific Aim 2:** The secondary aim of our study is to determine the mechanism by which PEACE exerts its anti-suicidal effect on patients after psychiatric hospital discharge. Based on available evidence, we hypothesize that the intervention plus standard psychiatric hospital discharge care exerts an anti-suicidal effect on patients after psychiatric hospitalization by improving social connectedness and engagement in care after discharge. We will assess this aim by performing the following analyses: First, we will perform an analysis to demonstrate whether there are greater improvements in social connectedness and engagement in care over time in patients assigned to the intervention versus control condition at one, three, and six months after discharge. For continuous variables measuring patient engagement, we will generate descriptive summary statistics (e.g., means and standard errors, medians) and graphical displays for each measure at baseline (assessment 1) and at assessments 2, 3, and 4. Second, using structural equation modeling, we will calculate mean differences in scores for each of our continuous measures at the one-, three-, and six-month assessment periods, as well as the associated 95% confidence intervals and *P*-values. For the categorical measure of patient engagement, we will use chi-squared tests to compare the proportion of patients adhering to their discharge plan between the two study arms at one-month after discharge. Third, we will assess whether social connectedness and patient engagement mediate the effect of the intervention on suicidal ideation, as measured by total BSS scores. In order to conduct this analysis, we will use structural equation modeling. We will use the maximum likelihood to account for any missing data. We will calculate the associated 95% CIs and *P*-values and will define a *P*-value of 0.05 to be statistically significant.

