### **Protected Health Information:**

We will administer several validated instruments to all enrolled patients at baseline and follow-up (one-, three- and six-month follow-ups). These instruments ask various questions related to self-harming thoughts or behavior and social connectedness. We will also ask patients to report on any non-VA healthcare utilization at one-, three- and six- month follow-ups. Demographic data and other baseline characteristics will be collected from the patient's electronic medical record at baseline. Information on VA healthcare utilization will be collected from the patient's electronic medical record at one- and three-month follow-ups. For patients assigned to the intervention arm, data on app utilization will also be downloaded from their app. All data will be collected solely for the purposes of this study. All study data will be collected using an electronic data-capture system. These data are stored on a local, secure research server that only study staff will have access to. All paper copies of study-related data, including consent and HIPAA forms, will be kept in a locked file cabinet, in a locked office, dedicated to this study. Only research staff will have access to this locked cabinet.

The My3 app will not store any PHI within the app. The app will only require access to the patient's contact list in order to facilitate a phone call between the patient and their support person.

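### The chart-based engagement measures have no baseline, so no change from baseline exists for them; the arm comparison stays valid, but precision and adjustment of the mediation path are lost

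*Combined protocol and SAP*

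**What the plan says.** Outcome Measures, Secondary Outcome (Patient Engagement), sets the timing for the whole construct: "We will measure patient engagement in treatment at assessment 1 as well as at assessments 2, 3 and 4". It treats engagement as patient activation, continuity of care and self-efficacy. The SRCS covers activation and self-efficacy, the BHS is added as clinical evidence of engagement, and three visit-based measures cover continuity of care.

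The visit-based measures are defined as follows:
- Continuity: whether the patient "received any MH outpatient treatment in the first month and between 1 – 3 m after discharge".
- Regularity: "The number of months in the 3 m after the baseline assessment in which the patient attended at least 1 MH visit".
- Intensity: "Measure of the total number of MH visits between initial entry into the" study and the last assessment.

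The section adds that "we will also evaluate evidence of disruptions of care including no-show and cancelled appointments", and gives the source: "We will abstract these measures from the electronic medical record".

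Statistical Considerations, Specific Aim 2, promises summaries of the continuous engagement variables and "graphical displays for each measure at baseline (assessment 1) and at assessments 2, 3, and 4". It then asks whether engagement improves more over time under PEACE, estimates mean differences at one, three and six months, and tests whether engagement mediates the effect on total BSS. Protected Health Information dates the chart collection: "Information on VA healthcare utilization will be collected from the patient's electronic medical record at one- and three-month follow-ups".

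**The concern.** The timing statement and the Aim 2 summary both presuppose an assessment 1 value for every engagement measure they cover. The visit-based measures only begin to accumulate at discharge or study entry, so an analyst following Aim 2 could not produce the promised baseline summary or a change score for them.

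Two things are at stake. First, earlier use of mental health care is likely to predict later use, and the plan has no such covariate to sharpen the comparison. Second, the mediation analysis relates engagement to the BSS. Randomisation does not protect that path, and prior use of care could influence both ends of it.

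**Working it through.** **The plan's own figure.** The only sample size is for the BSS (Sample Size, Table 3: effect size 0.5, four timepoints, correlation 0.5, 80% power, alpha 0.05, taken as two-sided). The two-group repeated-measures formula gives, per arm,

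n = 2(1.960 + 0.842)² × [1 + 3 × 0.5] / (4 × 0.5²) = 2 × 7.849 × 2.5 / 1 = 39.24, rounded up to 40.

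This matches the stated 40; the plan recruits 46 per arm to allow for dropout. No effect size, correlation or power is given for any engagement measure, so nothing in Table 3 changes.

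**Definitions against timing.**

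| Measure | Window in the protocol | Value at assessment 1 |
|---|---|---|
| SRCS | 0, 1, 3, 6 months (Table 2) | Yes |
| BHS | 0, 1, 3, 6 months (Table 2) | Yes |
| Continuity (yes/no) | Month 1, and months 1–3, after discharge | Undefined |
| Regularity (0–3) | 3 months after baseline | Undefined |
| Intensity (count) | Study entry to last assessment | Zero for everyone |
| No-shows, cancellations | None stated | Cannot be determined |

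The Aim 2 baseline summary is limited to continuous variables, so it conflicts with regularity and intensity. Continuity conflicts only with the general timing statement. For no-shows and cancellations the gap is a missing definition, not a contradiction. No section schedules collection of mental health use before the index admission.

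There is a related timing gap. Regularity and intensity give one value per patient, so they do not supply separate one-, three- and six-month values. VA chart collection is dated at one and three months, while intensity runs to the last assessment, at six months.

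**Size of chance imbalance in prior use.** With 46 per arm, in SD units:
- SE of the difference in mean prior use = √(2/46) = 0.2085.
- 95% range = ±1.96 × 0.2085 = ±0.41.
- P(|difference| > 0.25) = 2 × [1 − Φ(0.25/0.2085)] = 0.23.
- At an assumed prior-to-later correlation r = 0.5, the part carried into the later difference is 0.5 × 0.41 = ±0.20.

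The unadjusted later comparison has the same SE of 0.2085, hence its own range of ±0.41. The ±0.20 is a component of that range, not an addition to it.

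**Precision recoverable by adjustment.** Residual variance falls by r², and the 95% half-width becomes 0.41 × √(1 − r²):

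| r (assumed) | Variance reduction | 95% half-width (SD) |
|---|---|---|
| 0.3 | 9% | 0.39 |
| 0.5 | 25% | 0.35 |
| 0.6 | 36% | 0.33 |

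As an illustration only, take one timepoint, 40 per arm, a normal outcome and a hypothetical difference of 0.5 SD. Power = Φ(0.5/[√(1 − r²) × √(2/40)] − 1.96). This is 0.61 with no covariate, and 0.65, 0.73 and 0.88 at r = 0.3, 0.5 and 0.7. Visit counts and a 0–3 score are not normal, so these figures are approximate.

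**Mediation path.** Randomisation balances prior use, in expectation, for the arm-to-engagement comparison. It does nothing for engagement-to-BSS. The engagement section itself reports that symptom severity can keep patients from engaging, and that appointment intensity was higher in Veterans who reattempted. The covariate rule in Statistical Analyses adjusts only for variables that differ between arms at P < 0.05. A confounder of the engagement-to-BSS path can be evenly balanced between arms and still confound, so that rule would not reliably bring prior use in even if it were collected.

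**The case against.** The strongest reply is that this is a randomised trial and the Aim 2 estimators are between-arm contrasts: mean differences at follow-up and a one-month chi-squared test. Neither is stated to be a change from baseline, and neither needs one. If intensity is zero for everyone at entry, the difference in change equals the difference in level. This stands, and it defeats two stronger readings that a reader might infer.

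- *An effect on visit-based engagement cannot be shown.* It can; only a change from baseline cannot.
- *Chance imbalance in prior use biases the arm comparison.* It does not; it is ordinary sampling error already inside the confidence interval. Setting ±0.20 SD against the trial's 0.5 effect would also mix outcomes, since that 0.5 belongs to the BSS.

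It is also fair that the timing statement concerns engagement as a construct, and that the SRCS, labelled Engagement in Table 2, meets it at all four assessments.

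The covariate list is not closed. It names High Risk for Suicide List and Suicide Prevention Pathway status, which bear on scheduled visits, and Protected Health Information mentions unspecified baseline characteristics from the record. These are related to prior use but do not measure it, and no section names a look-back. The objection does not reach the unmet baseline summary or the mediation path.

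**Conclusion.** The inconsistency is definite: continuity, regularity and intensity have no baseline as defined, and no change from baseline can be calculated. The primary outcome, the SRCS and BHS analyses and the validity of the between-arm comparison of post-discharge levels are unaffected.

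The cost is lost precision on the chart measures (9% to 36% of residual variance for r between 0.3 and 0.6) and an unadjusted plausible confounder in the mediation analysis. The first rests on correlations that the documents do not give. The second rests on the reasonable but unquantified assumption that prior use of care relates to both later engagement and later BSS. The documents do not support calling Aim 2 untestable or the arm comparison biased.

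**What to change.** 1. Restrict the baseline and improvement-over-time wording for engagement, in the outcome section and in Specific Aim 2, to the SRCS and BHS.
2. Define continuity, regularity and intensity as post-discharge outcomes compared between arms, each with a stated window. Give no-shows and cancellations a window, and align VA chart collection with the end of the intensity window.
3. Abstract the same utilisation measures for a fixed pre-admission window, for example three months, and ask the existing non-VA care question for that window. Enter them as prespecified covariates in the Aim 2 chart-outcome and mediation models, regardless of baseline significance tests.

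Items 1 and 2 are mainly wording, with some later chart abstraction if intensity is kept to six months. Item 3 adds a modest look-back in a record already being abstracted for 92 patients, with no new visit or instrument, and can be applied to those already enrolled. Its limits are zeros that carry little information for patients new to VA care, and weaker recall of pre-admission non-VA care among those already enrolled. It reduces confounding of the mediation path but does not remove all of it.

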**Figure 5. Timeline of Assessments and Interventions**

dy = days; m = months; MH = Mental health; SDP = Standard psychiatric discharge practices; T0, T1, T2, T3 = assessment time points; wk = weeks

assessment) (3M) and assessment 4 (occurs six months after baseline assessment) (6M). These assessments will be conducted by the independent outcome assessor. The independent outcome assessor will conduct the baseline assessment in a private office on GE. We anticipate that, in most cases, assessment 1 will occur on the day before discharge. Depending on patient preference, the independent outcome assessor will conduct assessments 2, 3, and 4 in a private office on the WRJ VAMC campus, over the phone, or using VA Video Connect. The assessors will be blinded to study assignment and the patients will be instructed to not reveal their status to the assessor. All outcome variables will conform to the PhenX Common Data Elements (CDE) in order to improve our ability to compare our findings across other studies and maximize the impact of our results. The independent assessor will be blinded to study assignment. At each study visit, we will ask the assessor to guess the study assignment of the participant. We will consider that the blinding of the assessor was successful if the assessor is able to guess the assignment less than half of the time.

- Because app engagement will only be tracked in patients exposed to PEACE, we will ask that the study coordinator or study therapist (rather than the outcome assessor) administer the self-reported scale (AES) in order to avoid compromising the blinding of the outcome assessor. Quantitative measures of app engagement can be directly downloaded onto a secure server.
- As the WRJ VAMC is a rural medical center that serves a large geographic area (New Hampshire and Vermont), we anticipate that several enrolled patients will prefer phone (or VA Video Connect) over in-person follow-up. Fortunately, the assessment instruments that we selected for this study can be administered over the phone or in person. Furthermore, our decision to allow patients to participate in study follow-up by phone (or VA Video Connect) or in person is consistent with the study methods of the original WHO BIC trials.

**Intervention Training, Supervision, and Fidelity:** Given the systematic and structured nature of PEACE, it will be essential to maintain fidelity to the intervention and the manualized guide during the course of the trial. [name] will train the study staff in the delivery of PEACE, then the staff will complete several practice cases. [name] will review the staff's performance, provide feedback, and give additional training if necessary. As described above, PEACE incorporates MI techniques and [name] has experience in delivering MI. A fidelity-rating scale for PEACE was developed for this proposed trial (see Assessment Manual). The scale is adapted from the validated Yale Adherence and Competence Scale (YACS). The scale evaluates both adherence to the study protocol and the competence of the staff performing the intervention. The fidelity scale includes 15 items, of which 10 items pertain to the brief educational intervention and 5 items pertain to the regular contacts occurring after psychiatric hospitalization. The elements of the fidelity scale are based on the criteria outlined in the original WHO BIC protocol. Adherence to each of the 15 items on the scale will be rated on a 5-point scale ranging from "not at all" to "extensively." A random sample of 10% of cases will be selected for fidelity rating and the investigator ([name]) will sit in on these sessions as an observer in order to complete the rating scale. [name] will inform the intervention staff member if further adjustments are necessary to improve and maintain fidelity.

